6.1 Modified Intention-to-Treat

The mITT population will include all randomized subjects in whom treatment with i.v. study drug was initiated. Following the ITT principle, subjects will be analyzed according to the treatment they were assigned at randomization regardless of any randomization errors or amount of study drug infusion administered.

The mITT population will be the primary efficacy population, and all efficacy analyses and summaries will be performed using this population. All demographic and baseline summaries will also be summarized using the mITT population.

6.2 Per Protocol

The PP population will include all subjects in the mITT population who meet all the inclusion/exclusion criteria, received at least 96 hours over the course of 120 hours of study treatment (however, not excluding those subjects who die or are discontinued for an AE prior to receiving the full dose of 120 hours), and have a non-missing 6-month GOS score that was assessed at least 152 days from randomization. Subjects who initiate study drug infusion > 8 hours from time of injury but within 9 hours will be included in the PP population. The rationale for this is that the best available time of injury to the nearest hour is used at randomization, however a different time of injury may be determined later.

Study drug administration errors will be handled according to the following table when determining inclusion in the PP population:

Table 1
Handling of Study Drug Administration Errors in the Per Protocol Analysis

Medication Error Scenario		Inclusion in PP Population
Randomized to	Study Drug of Erroneously Received Bottle	
Placebo	Placebo	Included in placebo arm
Placebo	BHR-100	Not included
BHR-100	BHR-100	Included in BHR-100 arm
BHR-100	Placebo received as first administration of study drug or 2 or more bottles of placebo received at any time	Not included
BHR-100	1 placebo bottle received at any time except the first administration of study drug	Included in BHR-100 arm

Subjects at any site that is removed from the study for noncompliance with ABIC/EBIC/ Brain Trauma Foundation guidelines will be excluded from the PP population.

No imputation of the 6-month GOS score will occur in the PP analysis, but missing covariates will be imputed as described in Section 5.

The PP population will be used to perform confirmatory analyses of the primary efficacy evaluation.

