Subjects without a GOS response assessment at Month 6 but who have a death date from the Death Report eCRF within 6 months + 28 days of their randomization date (calculated as death date – randomization date + 1 \leq 208) will be assigned a Month 6 GOS response of Dead. Similarly, subjects without a GOS response assessment at Month 3 but who have a death date from the Death Report eCRF within 3 months + 28 days of their randomization date (calculated as death date – randomization date + 1 \leq 118) will be assigned a Month 3 GOS response of Dead.

Secondary Endpoint: Mortality at Month 1

Survival status from the date of injury (Day 1 of the study) until Day 30 (Month 1) will be monitored and recorded as lost to follow-up, consent withdrawn, alive, dead or other. Only subjects with a mortality assessment post-injury of alive or dead will be used in the assessment of mortality.

Secondary Endpoint: Mortality at Month 6

Survival status from the date of injury (Day 1 of the study) until Day 180 (Month 6) will be monitored and recorded as lost to follow-up, consent withdrawn, alive, dead or other. Only subjects with a mortality assessment post-injury of alive or dead will be used in the assessment of mortality.

Time to death

The time to death (in days) will be defined as:

$$\text{Date of death} - \text{date of TBI} + 1$$

If a subject does not die during the conduct of the study, they will be censored at the earliest (minimum) of their Month 6 GOS assessment date and end of study date, and censor time (in days) will be defined as:

$$\text{Minimum(month 6 GOS assessment date, end of study date)} - \text{date of TBI} + 1$$

Since subjects were not followed for death after their Month 6 GOS assessment, subjects who have a death recorded after the assessment will be censored on the date of their Month 6 assessment.

Exploratory Endpoint: CPP

The following formulae are used to derive CPP:

$$\text{Mean Arterial Pressure (MAP)} = \frac{2}{3} \text{ diastolic BP} + \frac{1}{3} \text{ systolic BP};$$

$$\text{CPP} = \text{MAP} - \text{ICP}.$$

MAP will be recorded as missing if either systolic BP and/or diastolic BP measurements are not recorded. CPP will be calculated where MAP and ICP have both been recorded; if either is missing the CPP will be recorded as missing.

Exploratory Endpoint: TIL

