9.5.2 Secondary Variables

Secondary efficacy parameters will be ranked as follows:

- 1) GOS-E at Month 6,
- 2) Mortality at Month 6 in mITT population (comparison of incidence of death),
- 3) GOS at Month 3,
- 4) GOS-E at Month 3,
- 5) Mortality at Month 1 in mTT population (comparison of incidence of death),
- 6) SF-36 mental composite score at Month 6,
- 7) SF-36 physical composite score at Month 6
- 8) SF-36 mental composite score at Month 3, and
- 9) SF-36 physical composite score at Month 3.

No confirmatory claims can be based on variables that have a rank lower than or equal to the variable whose null hypothesis was the first that could not be rejected at the p<0.05 significance level.

9.5.2.1 Mortality at Month 1, Month 6

These efficacy variables are obtained by collecting the survival status from the date of injury (Day 1 of the study) until Day 30 (Month 1) and Day 180 (Month 6) respectively as lost to follow-up, consent withdrawn, alive, dead or other. Every effort will be made to ascertain the survival status of subjects with status other than dead or alive, but in the absence of further information these observations will be omitted from the analysis. The 1-month mortality rate will be defined as the proportion of subjects at risk in the mITT population (subjects for whom the survival status at Day 30 is known) who died on or before Study Day 30. Similarly, the 6-month mortality rate will be defined as the proportion of subjects at risk in the mITT population who died on or before Study Day 180.

The hypothesis that the mortality rate observed in each treatment group is the same will be tested using the Fisher's Exact test.

$$\begin{array}{ll} \text{Null Hypothesis:} & H_0: p_1 = p_2 \\ \text{Alternative Hypothesis:} & H_1: p_1 \neq p_2 \end{array}$$

where p_1 = proportion of deaths in the BHR-100 treated group and p_2 = proportion of deaths in the placebo treated group.

A 2-sided, 5% significance level will be used to test the null hypothesis. If rejected ($p < 0.05$), it will be concluded that there is a statistically significant difference in the proportion of deaths between the 2 treatment groups.

In addition to the formal inference testing discussed above, 2-sided 95% confidence intervals for the difference in the proportion of deaths between BHR-100 and placebo treatment groups will be calculated.

Summaries of mortality at Months 1 and 6 will be presented for both the mITT and PP populations.

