	Statistic	BHR-100 (N=xx)	Placebo (N=xx)	Total (N=xx)
Subjects Who Were				
Randomized but Not Treated	n (%)	xx (xx.x %)	xx (xx.x %)	xx (xx.x %)
Modified Intention-to-Treat ¹	n (%)	xx (xx.x %)	xx (xx.x %)	xx (xx.x %)
Safety Population ²	n (%)	xx (xx.x %)	xx (xx.x %)	xx (xx.x %)
Per Protocol ³	n (%)	xx (xx.x %)	xx (xx.x %)	xx (xx.x %)
Study Completers ⁴	n (%)	xx (xx.x %)	xx (xx.x %)	xx (xx.x %)
Endpoint Completers ⁵	n (%)	xx (xx.x %)	xx (xx.x %)	xx (xx.x %)
Early Termination	n (%)	xx (xx.x %)	xx (xx.x %)	xx (xx.x %)
Reason for Early Termination				
Death	n (%)	xx (xx.x %)	xx (xx.x %)	xx (xx.x %)
Adverse Event(s)	n (%)	xx (xx.x %)	xx (xx.x %)	xx (xx.x %)
Withdrawal of Consent	n (%)	xx (xx.x %)	xx (xx.x %)	xx (xx.x %)
Protocol Violation	n (%)	xx (xx.x %)	xx (xx.x %)	xx (xx.x %)
Lost to Follow-up	n (%)	xx (xx.x %)	xx (xx.x %)	xx (xx.x %)
Discretion of the Investigator	n (%)	xx (xx.x %)	xx (xx.x %)	xx (xx.x %)
Discretion of the Sponsor	n (%)	xx (xx.x %)	xx (xx.x %)	xx (xx.x %)
Other	n (%)	xx (xx.x %)	xx (xx.x %)	xx (xx.x %)

¹ Modified Intention-to-Treat (mITT) Population includes all subjects who were randomized and in whom treatment with i.v. study drug was initiated (analyzed according to randomized treatment).

² Safety Population includes all subjects who received any study medication (analyzed according to actual treatment received).

³ Per Protocol Population includes all subjects in the mITT population who meet all inclusion/exclusion criteria, received at least 96 hours of study medication treatment, and have a non-missing 6-month GOS score.

⁴ Subjects are completers if they complete 6 months involvement in the study.

⁵ Subjects who provide a GOS at 6 months, including deaths carried forward to 6 months.

Note: Percentages are based on the number of subjects in each treatment group and overall in the population of interest.

Source: Listings 16.2.1.1, 16.2.1.2, 16.2.3.1

Program: xxxxxxx.sas, Output: xxxxxxx.rtf, Generated on: DDMONYYYY xx:xx, Page x of x

Table 14.1.1.4 Summary of Subject Status by Time (mITT Population)

Statistic	BHR-100 (N=xx)	Placebo (N=xx)	Total (N=xx)
Study Completers	n (%)	xx (xx.x %)	xx (xx.x %)
Early Termination	n (%)	xx (xx.x %)	xx (xx.x %)
Subjects Remaining in Study			
Day 1	n (%)	xx (xx.x %)	xx (xx.x %)
Day 2	n (%)	xx (xx.x %)	xx (xx.x %)
Day 3	n (%)	xx (xx.x %)	xx (xx.x %)
Day 4	n (%)	xx (xx.x %)	xx (xx.x %)
Day 5	n (%)	xx (xx.x %)	xx (xx.x %)
Day 6	n (%)	xx (xx.x %)	xx (xx.x %)
Day 15	n (%)	xx (xx.x %)	xx (xx.x %)

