[Note to Programmer: Dead is not an option on the GOS CRF page. This information can be read from the mortality or date of death details (for premature terminations due to death). This information should be combined for the derived datasets.]

Listing 16.2.6.1.5 Glasgow Outcome Scale, Glasgow Outcome Scale-Extended Narrative - Part 1

Treatment Group	Subject No.	Sex/ Age/ Race ¹	Month	Interview Date	Occupational Status	Summarize Subjects Work Capacity
BHR-100	xx-xxx	M/35/W (3,6)	DDMONYYY	xx		(Returned to normal level, Reduced, Only able to work in sheltered work shop or unable to work)

¹ M = Male, F = Female, W = White, B = Black, African American or of African Heritage, P = Native Hawaiian or Other Pacific Islander, A = Asian, N = American Indian or Alaska Native, Z=Not Allowed to Obtain, O = Other.

Program: xxxxxxx.sas, Output: xxxxxxx.rtf, Generated on: DDMONYYYY xx:xx, Page x of x

Listing 16.2.6.1.5 Glasgow Outcome Scale, Glasgow Outcome Scale-Extended Narrative - Part 2

Treatment Group	Subject No.	Sex/ Age/ Race ¹	Month	Date	Interview Social Skills	Has the subject resumed pre-injury level of social activities?
BHR-100	xx-xxx	M/35/W (3,6)	DDMONYYY		xx	(At least half as often, Less than half as often, Unable to or rarely participate)

¹ M = Male, F = Female, W = White, B = Black, African American or of African Heritage, P = Native Hawaiian or Other Pacific Islander, A = Asian, N = American Indian or Alaska Native, Z=Not Allowed to Obtain, O = Other.

Program: xxxxxxx.sas, Output: xxxxxxx.rtf, Generated on: DDMONYYYY xx:xx, Page x of x

Listing 16.2.6.1.5 Glasgow Outcome Scale, Glasgow Outcome Scale-Extended Narrative - Part 3

Treatment Group	Subject No.	Sex/ Age/ Race ¹	Month	Date	Interview Disruption or Strain	Summarize the subject's extent of disruption or strain:
BHR-100	xx-xxx	M/35/W (3,6)	DDMONYYY		xx	(Occasional (less than once per week), Frequent (once per week or more but tolerable), Constant (daily and intolerable))

¹ M = Male, F = Female, W = White, B = Black, African American or of African Heritage, P = Native Hawaiian or Other Pacific Islander, A = Asian, N = American Indian or Alaska Native, Z=Not Allowed to Obtain, O = Other.

Program: xxxxxxx.sas, Output: xxxxxxx.rtf, Generated on: DDMONYYYY xx:xx, Page x of x

Listing 16.2.6.1.5 Glasgow Outcome Scale, Glasgow Outcome Scale-Extended Narrative - Part 4

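### The SAP's per-protocol rule has no exemption for deaths in its 152-day GOS condition, so applied literally it drops early deaths that other parts of the SAP imply stay in

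*SAP*

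**What the plan says.** SAP 6.2 builds the PP set from the mITT set with three conditions joined by *and*: all eligibility criteria met; at least 96 hours of treatment; and a 6-month GOS, where the subject must "have a non-missing 6-month GOS score that was assessed at least 152 days from randomization". Deaths are mentioned once, in a parenthesis attached to the 96-hour condition: "not excluding those subjects who die or are discontinued for an AE prior to receiving the full dose of 120 hours". The section later adds: "No imputation of the 6-month GOS score will occur in the PP analysis". It names PP as the set for confirmatory analyses of the primary evaluation, and SAP 9 sets the level for those at 1%, two-sided.

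SAP Section 5 explains how a death gets a Month 6 score. The rule covers "Subjects without a GOS response assessment at Month 6 but who have a death date from the Death Report eCRF", and such subjects "will be assigned a Month 6 GOS response of Dead" if the death falls within 208 days of randomization. The programmer's note under Listing 16.2.6.1.4 says why this derivation is needed: "Dead is not an option on the GOS CRF page".

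Other parts of the SAP treat PP as a set that contains deaths:

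- SAP 9.5.2.1: "Summaries of mortality at Months 1 and 6 will be presented for both the mITT and PP populations".
- Table 14.1.1.3, footnote 3, defines PP with no 152-day condition, asking only that subjects "received at least 96 hours of study medication treatment, and have a non-missing 6-month GOS score". Footnote 5 counts deaths as providing a 6-month GOS.
- Figure 14.2.1.3, the PP chart of GOS, has a Dead/Vegetative State category.

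**The concern.** A subject who dies on Day 10 has an assigned Dead score and no assessment, so no assessment date can reach day 152. Taken at its word, the third condition excludes that subject from PP.

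Death is an outcome that treatment may change. Removing deaths conditions the confirmatory comparison on survival, takes unequal numbers from the two arms whenever the drug affects mortality, and takes much of the mortality effect out of the proportional odds model. PP mortality at Month 1 would be zero in both arms by construction. The SAP would also hold two different PP definitions, one in 6.2 and one in the disposition table.

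**Working it through.** **1. What the wording does to four illustrative subjects**

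| Subject | 6.2 read literally | Parenthesis stretched over the whole sentence | Table 14.1.1.3 footnotes |
|---|---|---|---|
| Dies on Day 3, during infusion | Out: no assessment by day 152 | In | In, if the parenthesis also covers the 96-hour condition there |
| Completes infusion, dies on Day 10 | Out | Out: death came after the 120 hours | In |
| Alive, GOS visit at day 140 | Out: too early | Out | In |
| Alive, GOS visit at day 185 | In | In | In |

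The second row is decisive. Even the generous reading of the parenthesis does not rescue a death after the infusion and before day 152. It would keep deaths during infusion and drop later ones, which is not a coherent population.

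**2. Reproducing the design figure**

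Inputs from SAP 3.1: placebo 31% good recovery (GR), 21% moderate disability (MD), 19% severe disability (SD), 29% vegetative or dead; common odds ratio 1.5; 590 per arm; two-sided 1%; 90% power. Applying 1.5 to the cumulative odds gives BHR-100 40.3 / 21.6 / 16.7 / 21.4%.

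N = 12(z₁₋α/₂ + z_power)² / [ln(OR)² (1 − Σp̄ᵢ³)] = 12(2.576 + 1.282)² / [0.1644 × (1 − 0.0766)] = 1176, against 1180 stated. Power at 590 per arm is 90.1%. The plan's figure reproduces.

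**3. Literal-reading scenario**

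The documents give neither the split of vegetative and dead nor the timing of deaths. I let early deaths be 70–100% of that category in both arms. I removed the expected deaths, refitted the proportional odds model to the remaining expected counts, and took

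power = Φ(|ln OR| √V − 2.576), with V = n₀n₁N / [3(N+1)²] × (1 − Σp̄ᵢ³).

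| Early deaths as share of vegetative/dead | Removed, placebo | Removed, BHR-100 | Total (of 1180) | Left | PP odds ratio | Power at 1% |
|---|---|---|---|---|---|---|
| 100% | 171 | 126 | 297 (25.2%) | 883 | 1.355 | 43% |
| 90% | 154 | 114 | 268 (22.7%) | 912 | 1.382 | 52% |
| 80% | 137 | 101 | 238 (20.2%) | 942 | 1.406 | 60% |
| 70% | 120 | 88 | 208 (17.6%) | 972 | 1.425 | 67% |

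First row: n₀ = 418.9, n₁ = 463.7, Σp̄ᵢ³ = 0.145, so V = 62.6. Then 0.304 × 7.91 − 2.576 = −0.17, and Φ(−0.17) = 0.43.

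**4. If the drug only prevents deaths**

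Take 26% placebo deaths and 3% vegetative (an assumed split of the 29%), and let BHR-100 cut deaths by 7.6 points (29.0 − 21.4). The odds ratio among survivors depends on where the rescued patients land:

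| Rescued patients become | Odds ratio, survivors only |
|---|---|
| Spread like other survivors | 1.00 |
| All severely disabled | 0.81 |
| Half vegetative, half severely disabled | 0.78 |
| All good recovery | 1.20 |

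If the whole 29% are early deaths and all rescued patients become severely disabled, the odds ratio is 1.12 with deaths kept and 0.79 without them, so the direction reverses.

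**The case against.** The best defence is that deaths were plainly meant to stay. A subject who dies within 120 hours can never have a visit at day 152, so if the third condition excluded deaths, the words in the parenthesis about subjects who die would do nothing. PP mortality tables would be pointless without deaths. The table footnotes count deaths as having a GOS. And 152 is 180 − 28, the early edge of the protocol's Month 6 window, which suggests (the SAP does not say so) that the clause was written to screen out visits made too soon. I accept all of this as evidence of intent. The figure legend is weaker evidence, since its Dead/Vegetative category is the same as in the mITT charts and would exist with vegetative patients alone.

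A reader might go further and infer that the SAP plans a survivors-only confirmatory analysis. The documents do not support that: it follows from one clause read alone, against several others. A reader might also infer that the ban on imputed scores removes deaths. That does not follow clearly either. Section 5 describes imputation as carrying Month 3 forward or predicting from the model, and handles deaths under a separate heading. Footnote 5 of Table 14.1.1.3 does speak of deaths as carried forward, however, so the point deserves a sentence. Finally, the PP odds ratio for a mortality-only effect is not necessarily 1.0; that holds only when rescued patients spread like other survivors.

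The defence is also right that the primary mITT analysis, the 0.0098 criterion and the ranked secondary tests are untouched, and that populations are assigned at a blinded review meeting where the problem might be noticed. None of this repairs the text: intent is not what gets programmed, and that meeting needs one rule to apply.

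**Conclusion.** The concern holds as an internally inconsistent rule, and in that sense 6.2 is wrong as written. Followed literally, it excludes deaths before day 152, while the SAP's PP mortality tables and disposition footnotes imply they are included.

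The size is that of a scenario, not a forecast. At the design assumptions, the literal rule would remove about 18–25% of subjects, lower the PP odds ratio from 1.5 to about 1.36–1.43, and lower power from 90% to about 43–67%. This rests on the assumed 70–100% share of early deaths in the vegetative/dead category, and on a PP set that loses nobody for other reasons. The 90% is the design power for all 1,180 treated subjects; the SAP states none for PP. The harm is confined to the confirmatory PP analyses, where a benefit could look weaker than it is, vanish or reverse.

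**What to change.** In SAP 6.2, replace the third condition with: *have a 6-month GOS that is either Dead (assigned under Section 5, whatever the day of death) or assessed at a visit at least 152 days from randomization*. Add one sentence saying that a Dead score assigned under Section 5 is not imputation for the purposes of the PP analysis. Bring footnote 3 of Table 14.1.1.3 into line with the new wording, including the 152-day minimum for visits.

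The cost is two sentences and one footnote, with no new data and no change to sample size or the primary analysis. It should be done before the blinded meeting assigns populations and before unblinding, so that nobody can say the rule was settled with results in view.

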6.3 Safety

The safety population will include all subjects who received any study drug. Subjects will be analyzed according to treatment received regardless of the randomization schedule. If a subject received *any* amount of BHR-100, they will be summarized according to treatment BHR-100 for the safety population.

The safety population will be used for all summaries of safety data and treatment exposure data.

7 INTERIM ANALYSIS

A formal interim analysis will be performed once the first 200 subjects in each treatment arm (total of 400 subjects) have reached a study endpoint (death, lost to follow up, or completed the study and assessed for the 6-month GOS). The database used for the interim analysis will only contain these 400 subjects.

At the planned interim analysis, the test statistic based on the effect size (common odds ratio) will be compared to the critical value shown below. If the test statistic exceeds the critical value, the unblinded study statisticians will discuss the continuation of the trial with the DSMB and the DSMB will inform the Sponsor. In order to stop the trial at the interim analysis, the significance level will need to be less than the critical p-value (i.e. $p < 0.0003$).

At the planned interim analysis, a 2-sided test will be performed to detect either an increase or decrease in the common odds ratio, as described in the section of this document on primary end point analysis, section 9.5.1. In order to preserve the over-all type I error rate at 1%, the critical value for the test statistic will be inflated above 2.575, the value that would be used if no repeated testing were used. The actual critical values and p-values will be computed using statistical methods for group sequential testing with the O'Brien Fleming method.

If the p-value from the test of the null hypothesis of no treatment difference is less than 0.0003 at the interim analysis, the study may be stopped for efficacy. Table 2 indicates the critical values, p-values and cumulative type I error for this study:

Table 2
Critical Values and p-Values of Interim and Final Analyses

Interim and final analyses	Total sample	Critical Value	p-value	Cumulative Type I Error
Interim (1)	400	3.65	0.0003	0.0003
Final (2)	1180	2.58	0.0098	0.0101

No formal stopping rule for futility will be established for this study. An assessment of conditional power at the interim analysis will be provided to the DSMB for consideration with the safety summaries in the evaluation of the overall risk/benefit of the study treatment.

Under the condition that the proportional odds model assumption holds, the statistical power to reject the null hypothesis of equal six-month GOS is shown below under a variety of scenarios (Table 3).

Conditional power is the estimate of the power to observe a difference in treatment groups different from that observed at the interim analysis. The conditional power is calculated based upon the observed critical value and measure of the completion of the trial. Methods for this calculation have been proposed by Lan, DeMets and Halperin and Lan, Simon and Halperin.

Table 3
Futility Analysis: Power to Reject Null hypothesis under Various Scenarios

Common odds ratio ¹		Power at interim and final analysis	
Placebo	BHR-100	Interim analysis ²	Final analysis ³
1.0	1.27	1.54%	39.36%
1.0	1.50	10.93%	90.66%
1.0	2.33	88.49%	99.99%

¹ A common odds ratio of 1.27, 1.5 and 2.33 is equivalent to a 5%, 10% and 20% effect size respectively.

² Interim analysis is based on the assessment of 400 completed subjects (200 in each arm).

³ Final analysis is based on total study recruitment at 1180 treated subjects with 590 in each arm. This sample size is calculated based on the defined baseline outcome distribution (31% Good Recovery, 21% Moderate Disability, 19% Severe Disability and 29% Vegetative State/Death) to detect a common odds ratio of 1.5 of improvement in outcome with 90% power and 1% significance level (2-sided).

In the event that the *final* primary efficacy analysis does not show statistical significance at the study-wise 1% significance level (i.e. the final analysis p-value is not less than 0.0098) a final adjusted p-value will be calculated and the result considered statistically significant at the 5% level if the adjusted p-value is less than 0.05. The adjusted p-value will be calculated using EAST (Cytel Statistical Software, Cambridge, MA) or other appropriate statistical software package to adjust for the interim analysis.

